### **11.11 Physical Examination**

Screening physical examinations will include, at a minimum, assessment of the following: general appearance, head, ears, eyes, nose and throat, neck (including thyroid and lymph nodes), respiratory system, cardiovascular system, gastrointestinal system, renal system, neurological system, musculoskeletal system, skin, and any other focused assessments suggested by the presence of specific symptoms.

Targeted physical examination will include general appearance, head, ears, eyes, nose and throat, respiratory system and any other focused assessments suggested by the presence of specific symptoms.

All physical examinations will be conducted by a licensed physician within the time windows specified in the SoA. Physical examinations may also be performed at various unscheduled timepoints if deemed necessary by the Investigator.

All CS findings post-dose will be recorded as AEs.

### **11.12 Nasal Examination**

A macroscopic nasal examination will be performed by conventional anterior rhinoscopy with otoscope with attached otic speculum to assess swelling of the mucosa, erythema, and

---

secretions at the time of physical examination, at time points specified in the Schedule of Assessments ([Appendix 21.1](#)).

All events will be graded for severity as mild, moderate, or severe in the opinion of the investigator (or delegate) ([Section 12.2.112.2.1](#)) and recorded as AEs.

### 11.13 Vital Signs

Vital signs assessments will include systolic and diastolic blood pressure, pulse rate, respiratory rate (RR), and oral temperature. Participants should be resting in a supine/semi-supine position for at least 5 minutes prior to and during vital signs measurements.

Vital signs assessments may be repeated once, if abnormal values (outside of site's normal ranges) were recorded in the first instance, at the discretion of the PI (or delegate).

All CS findings post-dose will be recorded as AEs.

Site normal vital signs ranges are as follows:

- Temperature:  $\geq 35.5 \text{ } ^\circ\text{C}$  to  $\leq 37.7 \text{ } ^\circ\text{C}$
- Pulse Rate:  $\geq 45 \text{ bpm}$  to  $\leq 100 \text{ bpm}$
- Respiratory Rate:  $\geq 12$  to  $\leq 22 \text{ breaths/min}$
- Systolic Blood Pressure:  $\geq 90 \text{ mmHg}$  to  $\leq 160 \text{ mmHg}$
- Diastolic Blood Pressure:  $\geq 50 \text{ mmHg}$  to  $\leq 95 \text{ mmHg}$

### 11.14 Electrocardiogram

12-lead ECG will be performed at Screening, and at End of Study for both study parts. At each protocol scheduled timepoint, ECGs will be performed in triplicate with each replicate separated by at least 1 minute and the full set of triplicates completed within 5 minutes. The mean value for the triplicate will be utilised. Each ECG will be conducted in a supine (or semi-supine) position after the participant has been resting for at least 5 minutes in a quiet setting without distractions (e.g., television, mobile phones).

Site normal ranges for ECG parameters are as follows:

- HR: 45 bpm to 100 bpm
- PR:  $\geq 120 \text{ msec}$  to  $\leq 220 \text{ msec}$
- QRS:  $< 120 \text{ msec}$
- QTcB & QTcF:  $\leq 470 \text{ msec}$  (females) or  $\leq 450 \text{ msec}$  (males)

ECGs will be interpreted, signed, and dated by the PI (or delegate). The ECGs will be classified as normal, abnormal NCS, or abnormal clinically significant. In addition, ECG parameters of ventricular HR, PR interval, QRS duration, QTcB and QTcF will be noted on the eCRF.

Abnormal ECGs that are clinically significant will be repeated. In the case of evident bad quality (e.g., muscle tremor) of the tracing, an ECG will be repeated. Abnormal ECGs that are NCS may be repeated in at the Investigator's discretion. Repeat assessments will be performed in triplicate.

---

Additional ECGs may be performed at any time during the study as required, at the discretion of the PI (or designee).

All CS findings post-dose will be recorded as AEs.

### **11.15 Nasal Symptoms by Sino-Nasal Outcome Test**

Nasal symptoms and social/emotional consequences will be assessed using the Sino-nasal outcome test (SNOT-22) at different timepoints, as presented in the SoA ([Appendix 21.121.1](#)). Participants will be asked to rate their experience of each of 22 listed symptoms on a scale of 0-5 based on symptoms over the preceding 2 weeks. The rating scale is as shown below:

- 0 = No Problem
- 1 = Very Mild Problem
- 2 = Mild or slight Problem
- 3 = Moderate Problem
- 4 = Severe Problem
- 5 = Problem as bad as it can be

Participants will also be asked to identify up to 5 of the most important issues affecting them, from the list of 22 symptoms.

### **11.16 Study Diary**

Participants will be provided with a study diary on Day 1 to record any solicited and/or unsolicited AEs, and to record concomitant medication usage. Participants will be instructed on use of the diary by site staff during in-person visits.

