**Table 5-A LMN-301 COV01 Study Objectives and Endpoints**

Objectives	Endpoints
Primary	
To determine the safety and tolerability of single and multiple doses of intranasally delivered LMN-301	
 
Safety and tolerability of single and multiple doses of intranasally administered LMN-301 as measured by: 
 
The occurrence of solicited AEs for 28 days after the first dose of LMN-301
 
The occurrence of unsolicited AE/SAEs for up to 28 days after the first dose of LMN-301
 
Discontinuation
 
Changes from baseline in vital signs, safety laboratory parameters, ECG parameters and nasal symptoms using the Sino-nasal outcome test
 
 
 

Secondary	
To determine the persistence profile of LMN-301 in the nasal mucosa following single and multiple doses	
 
Detect the presence of LMN-301 in nasal mucosal lining fluid samples collected from study participants
 

Exploratory	
To detect the presence of LMN-301 and anti-drug antibodies in serum	
 
Detection of LMN-301 virus-binding proteins and anti-virus binding protein Immunoglobulin G (IgG) in serum samples
 

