## 6.7 Treatment Allocation

All study participants who sign an informed consent form at screening will receive a unique sequential number (i.e., a screening number). Participants will be allocated to the next available treatment group in the order they are screened. As this is an open-label study, no randomisation or blinding will occur.

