### 10.2 Part A Sentinel Cohort (open-label, one fixed dose)

In Part A, 5 sentinel participants will be observed for 24 hours as inpatients, and then followed for 14 days. Protocol-specified evaluations and procedures will be performed on Day 1-2 and weekly or bi-weekly as outlined below and in the SoA ([Appendix 1](#)).

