#### 10.3.4 Days 15-17

Solicited and unsolicited AEs/SAEs and concomitant medications will be recorded daily using the participant diary

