### 12.3 Procedures and Time Period for Detecting Adverse Events

The Investigator or designee is responsible for detection, recording and reporting of events that meet the criteria and definition of AEs.

As a consistent method of soliciting AEs, the participant shall be asked a nonleading question such as: "How do you feel?".

The presence or absence following 'solicited AEs' will be assessed by direct questioning:

- stuffy nose
- runny nose
- sneezing
- nasal irritation
- nasal tenderness/ pain
- loss of smell
- sore throat/ scratchy throat
- cough

Detection and recording of study related AEs and SAEs extends from the signing of the consent form until completion of the last study related procedure (including follow-up for safety assessments). Any AE reported or observed at or after the start of dosing with study drug will be recorded as a treatment-emergent AE (TEAE) or SAE.

Any pre-existing conditions or signs and/or symptoms present in a participant prior to the start of the study (i.e., before informed consent), should be recorded as medical history. In addition, any change in health status that is reported or observed after informed consent but prior to starting study drug and is deemed by the study Investigator to be "not related" to study procedures, will be documented as medical history.

A post-study AE/SAE is defined as any event that occurs outside of the nominal AE/SAE study detection period. Investigators are not obligated to actively seek AEs/SAEs in former study participants. However, if the Investigator learns of any SAE, including a death, at any time after a participant has completed the study and he/she considers the event reasonably related to the investigational product, the Investigator will promptly notify the Sponsor.

Participants must be provided with an “Emergency Wallet Card” indicating the name of the investigational product, the study number, the Investigator’s name, a 24-hour emergency contact number, and, if applicable, excluded concomitant medications.

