4. Intranasal mucosal lining fluid sample collected prior to dosing and 2 hours ( $\pm 15$  mins) after dosing on Day 1
5. Intranasal mucosal lining fluid sample collected prior to dosing on Days 3 (Groups 2 and 3), 4 (Group 1), prior to dosing on Day 7 and on Day 14
6. Group 1: Participants in Group 1 will be dosed once every third day during Day 1-12
7. Group 2: Participants in Group 2 will be dosed once **every other day** during Day 1-12
8. Group 3: Participants in Group 3 will be dosed once **every day** during Day 1-12
9. Participants will be provided with a diary to record any solicited and/or unsolicited AEs, and to record concomitant medication usage. AEs to be recorded on each Day 1-28.
10. Solicited local AEs: stuffy nose, runny nose, sneezing, nasal irritation, nasal tenderness/pain, loss of smell, sore throat scratchy throat, cough
11. Vital signs be performed at Day 1 pre-dose, 15 min ( $\pm 5$  min), 30 min ( $\pm 5$  min), 1 hr ( $\pm 15$  min), 4 hr post-dose ( $\pm 15$  min), and once on Days 3 (Groups 2 &3 only), 4 (Group 1 only), 7, 14 and 28
12. Targeted physical examination to be performed within 1 hour pre-dose on dosing days. Nasal examination to assess swelling of the mucosa, erythema, and secretions to be performed using nasal speculum and headlight within 1 hour pre-dose and 3 hours post dose on Day 1 and then at 3 hours post dose on Day 3 (Groups 2 and 3 only) or Day 4 (Group 1), 3 hours post dose on Day 7, 3 hours post dose on Day 10 (Group 1) or Day 11 (Group 2 and 3) and on Day 14.
13. Urinalysis and ECG to be performed at Screening and at End of Study
14. Covid-19 RAT test to be performed at screening and prior to dosing on Day 1 Day 3 (Groups 2 and 3 only) or Day 4 (Group 1), Day 7, Day 10 (Group 1) or Day 11 (Group 2 and 3) and Day 14. Participants testing positive will not be permitted to participate in the study.
15. Urine pregnancy test to be performed any time prior to dose administration on Day 1; otherwise, may be performed any time on the scheduled day.
16. To be performed within 1 hour prior to dose administration on dosing days; otherwise, may be performed any time on the scheduled day.
17. Sino-Nasal Outcome Test to be performed at 2 hours ( $\pm 15$  mins) post-dose on dosing days; otherwise, test may be performed at any time on the scheduled day.
18. Update only.
19. Site staff to review diary at each clinic visit. Diary to be collected at the final EoS visit on Day 28.

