13.1 Adverse Events

AE verbatim terms will be coded using the version 25.1 of the Medical Dictionary for Regulatory Activities (MedDRA). AEs and SAEs are defined in the study protocol.

- Treatment Emergent Adverse Events (TEAEs) are defined as adverse events that occurred or worsened from the first administration of study drug. If determination cannot be made as to whether the event is treatment emergent due to missing or incomplete data, the adverse event will be treated as treatment emergent.
- Treatment-Related AEs are defined as any TEAEs reported with the causality of “Related” to study treatment.
- Solicited AEs will be assessed by direct questioning and include stuffy nose, runny nose, sneezing, nasal irritation, nasal tenderness/pain, loss of smell, sore/scratchy throat, and cough.
- Unsolicited AEs include all other AEs not classified as Solicited adverse events.

All AE summaries will be restricted to TEAEs only.

The TEAE summaries will include:

- Overall Summary of TEAEs
 - TEAEs
 - TEAEs by Severity (Grade 1 to Grade 5)
 - TEAEs by Relationship
 - Treatment Related TEAEs
 - Serious TEAEs
 - Treatment Related Serious TEAEs
 - Solicited TEAEs
 - Unsolicited TEAEs
 - TEAEs leading to Death
 - TEAEs leading to Study Withdrawal

The following table summaries will be presented by SOC and PT by treatment groups defined in Section 4.6:

- TEAE summary by SOC and PT
- TEAE summary by SOC, PT and Severity
- TEAE summary by SOC, PT and Relationship
- Treatment Related TEAE summary by SOC and PT
- Treatment Related TEAE summary by SOC, PT and Severity

- Serious TEAE summary by SOC and PT
- Treatment Related Serious TEAEs summary by SOC and PT
- Solicited TEAE summary by SOC and PT
- Unsolicited TEAE summary by SOC and PT

The above items will be presented using summary tables, which will include the number of participants (%) experiencing an event and the number of events. If a participant experienced the same adverse event multiple times, this will only be counted once for the purpose of counting the number of participants experiencing that adverse event. Summary tables will be done for the SS population for treatment groups defined in Section 4.6. Where SOC and PT are reported, the display will be sorted by the descending order of occurrences of SOC and PT, followed by alphabetical sorting. In Part B, summaries will be sorted based on counts in the overall treatment group.

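### In Part B, the 28-day solicited-AE incidence mixes drug reactions with ordinary nasal symptoms, and the SAP does not separate on-drug from off-drug onsets

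*Protocol*

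**What the plan says.** The first component of the primary endpoint is "The occurrence of solicited AEs for 28 days after the first dose of LMN-301" (Protocol Table 5-A; repeated in SAP 2.2.1). There is no comparator: "As this is an open-label study, no randomisation or blinding will occur" (Protocol 6.7).

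The eight items are stuffy nose, runny nose, sneezing, nasal irritation, nasal tenderness or pain, loss of smell, sore or scratchy throat, and cough. They are asked by direct questioning (Protocol 12.3) and recorded in a diary: "Participants will be provided with a study diary on Day 1 to record any solicited and/or unsolicited AEs" (Protocol 11.16). The Screening list in Protocol 10.1 does not include them, and Protocol 10.3.1 lists them for Day 1 without placing the question before dosing. For Part B, footnote 9 of Table 21-B says "AEs to be recorded on each Day 1-28". One section heading differs: "10.3.4 Days 15-17".

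Treatment emergence is defined in two ways. Protocol 12.3 has "Any AE reported or observed at or after the start of dosing with study drug will be recorded as a treatment-emergent AE". SAP 13.1 has "adverse events that occurred or worsened from the first administration of study drug", and counts an event as treatment-emergent when incomplete data leave this undecided. The table of changes in SAP 16 does not mention the difference.

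SAP 13.1 tabulates solicited events by SOC, PT and treatment group, with no division by time. Protocol 8.5 puts the last dose on Day 10 (Group 1), Day 11 (Group 2) and Day 12 (Group 3).

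**The concern.** The solicited items overlap with two sources of events. Protocol 4.3 expects sneezing, nasal discharge, tenderness, pain and irritation from the product. Protocol 12.4 treats cough, runny nose, sneezing and sore throat as signs of an ordinary upper respiratory infection. With no control arm and no pre-dose record of the same items, one pooled incidence cannot show how much belongs to the product.

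More than half of the Part B window lies after the last dose, so much of the background would be gathered off drug and still be reported as treatment-emergent. Groups are filled in sequence, Group 1 first, so dosing frequency is tied to calendar time. A group followed during a cold season could look less tolerable for that reason alone. At stake is the tolerability rate that readers will attribute to LMN-301.

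**Working it through.** **The plan's own figures.** Protocol 13.1 and SAP 3 give probabilities of seeing at least one SAE at a 10% rate. They reproduce: 1 − 0.9^35 = 97.5% and 1 − 0.9^30 = 95.8%. They concern SAEs. The plan has no figure for solicited symptoms or their background.

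**Days after the last dosing day (Protocol 8.5).**
- Group 1: 28 − 10 = 18, or 18/28 = 64%
- Group 2: 28 − 11 = 17, or 17/28 = 61%
- Group 3: 28 − 12 = 16, or 16/28 = 57%

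**Background incidence (rates assumed).** Let h be the daily probability that any of the eight symptoms starts spontaneously, constant and independent over days. Incidence over d days is 1 − (1 − h)^d. The share first arising after Day 12 is 1 − (12-day incidence ÷ 28-day incidence).

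| h per day | 28 days | Expected of 30 | 12 days | Share after Day 12 | 14 days |
|---|---|---|---|---|---|
| 0.5% | 13.1% | 3.9 | 5.8% | 55% | 6.8% |
| 1% | 24.5% | 7.4 | 11.4% | 54% | 13.1% |
| 2% | 43.2% | 13.0 | 21.5% | 50% | 24.6% |

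**What the pooled table cannot separate.** If the drug independently causes a solicited event in a proportion r, observed incidence is 1 − (1 − q)(1 − r), where q is the 28-day background. For an observed 43.2%, r = 1 − 0.568/(1 − q). This gives r = 35% at q = 13.1%, 25% at q = 24.5%, and 0% at q = 43.2%. All three produce the same planned table.

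**What a split would show.** Suppose every drug-caused onset falls in Days 1–14. The expected share with an onset in Days 1–14 is 1 − (1 − q14)(1 − r), and in Days 15–28 it is q14, the 14-day background:
- h = 0.5%, r = 34.6%: 1 − 0.932 × 0.654 = 39% against 7%
- h = 1%, r = 24.8%: 1 − 0.869 × 0.752 = 35% against 13%
- h = 2%, r = 0: 25% against 25%

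The same pooled 43% becomes three visibly different patterns.

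**The internal dose-frequency contrast.** Group 1 against Group 3 (10 against 10, two-sided Fisher exact test at 5%) has 13% power for 20% versus 50% and 43% for 20% versus 70%. It is also tied to contact: through Day 14, Groups 1, 2 and 3 have 5, 7 and 13 clinic visits. Exact 95% intervals are wide: 4/10 gives 12–74% and 12/30 gives 23–59%.

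**The case against.** Much of the other side stands, and it limits the point.

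- **A reader might infer that nothing is known before dosing.** That is not so. SNOT-22 at Screening rates 22 symptoms over the preceding two weeks, and its change from baseline is part of the primary endpoint. A nasal examination and a targeted physical examination precede the first dose, and medical history is updated on Day 1. These remain partial: Screening may be 28 days earlier, the Day 1 SNOT-22 comes two hours after dosing, and the nasal examination looks at swelling, erythema and secretions.
- **A reader might infer that Protocol 12.3 turns every existing symptom into an adverse event.** The next paragraph there sends pre-existing symptoms, and unrelated changes between consent and dosing, to medical history. The wording still differs from the SAP, and worsening is hard to judge without a severity for the same items.
- **A reader might treat the eight symptoms as independent over 8 × 28 = 224 symptom-days.** At 1% per symptom per day that gives 1 − 0.99^224 = 89%. Protocol 12.4 expects such symptoms to occur together and be recorded as one diagnosis where possible. With full clustering the same rate gives 25%, so the 89% is not supported. Recording a diagnosis may also move a cold out of the solicited table.
- **A reader might apply the 28 days to the whole study.** In Part A, "5 sentinel participants will be observed for 24 hours as inpatients, and then followed for 14 days", so the calculation concerns Part B only.
- **A reader might conclude that diaries stop on Day 17.** Protocol 10.3, 10.3.1, 10.3.5 and Table 21-B all carry recording to Day 28. The heading is an editorial slip.
- **The split is not a clean own control.** Days 1–14 contain nearly all visits and diary reviews, and nasal swabs on Days 1, 3 or 4, 7 and 14. Between Day 14 and the Day 28 visit there is diary entry only.

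Causality ratings, onset times, exclusion of allergic and nasal disease, and COVID-19 testing also help. They reduce or annotate background without measuring it, and causality is rated unblinded. An uncontrolled design is a declared choice for a small descriptive Phase 1 study, and no control arm is asked for here.

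**Conclusion.** The concern holds for Part B in limited form. The pooled 28-day solicited incidence combines drug reactions with ordinary symptoms, and 57–64% of the window follows the last dosing day. On assumed any-symptom onset rates of 0.5–2% per day, 13–43% of participants (3.9–13.0 of 30) would have a solicited event with no drug effect, about half of them first arising after Day 12. The rates are illustrative, since the documents give none, and they assume constant, independent daily onset. Eligibility criteria could put the true rate below this range.

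This does not make the study uninterpretable. It means that the planned table alone should not be read as a tolerability rate for LMN-301, and that a table from data already collected would make it more informative.

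**What to change.** 1. **SAP 13.1: add one table.** Tabulate Part B solicited treatment-emergent events by onset in Days 1–14 (the dosing period plus a 2–4 day lag) and Days 15–28 (off drug), by group and overall, with participant counts and days at risk. Protocol 12.4 records each change in severity as a new event, so join continuous records into one episode before assigning onset. Call it a descriptive within-participant comparison. State both biases: delayed reactions raise the Days 15–28 column and shrink the contrast, while more visits, questioning and nasal swabs raise the Days 1–14 column and enlarge it. Onset times (SAP 13.1) and dosing dates (SAP 12) are already collected, so the cost is SAP wording and one table before database lock.
2. **Day 1 check.** For participants not yet dosed, ask the eight items with severity before the first dose, so that new or worse symptoms can be recognised. This needs an amendment and a few minutes per participant. SAP 16 says all enrolled subjects had received a dose, so this may serve only later studies. A pre-dose run-in diary is not needed.
3. **Definitions.** Reconcile the treatment-emergent wording of Protocol 12.3 with SAP 13.1, or list the difference in SAP 16.
4. **Editorial.** Reconcile the heading of Protocol 10.3.4 with diary recording through Day 28.

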### **11.17 Pharmacokinetic Assessments**

#### *11.17.1 Blood*

Whole blood samples will be collected and processed to obtain serum for the determination of LMN-301 levels on Days 1 (pre- and post-dose), 2 and 8 for the sentinel cohort and on Days 1 (pre- and post dose), 3 or 4, 7 and 14 for the multi-dose cohort. Serum samples will be stored at -80°C until shipped to Lumen Bioscience (Seattle, USA) for subsequent processing and analysis. With the participant's approval, de-identified leftover samples may be stored at Lumen Bioscience indefinitely and used for future research studies related to the development of LMN-301. This future research will not include genomic sequencing. Detailed instructions for the collection, processing, and shipment of samples for LMN-301 PK will be described in the study Laboratory Manual.

#### *11.17.2 Nasal Secretions*

Nasal mucosal lining fluid (MLF) samples will be collected on Days 1 (pre- and post-dose), 2 and 8 for the sentinel cohort and on Days 1 (pre-and post-dose), 3 or 4, 7 and 14 for the multi-dose cohort. Sampling will alternate between right and left nostrils during sequential sample collection time points.

MLF samples will be collected using the Nasosorption™ FX·I device (Hunt Developments

(UK), United Kingdom). This device consists of a synthetic absorptive matrix (SAM™) swab to absorb MLF from the mucosa within the nose. MLF will be collected by research staff inserting the swab into the participant's nasal cavity for a period of 60±10 seconds in order to obtain the sample. Samples will be processed and stored, in accordance with the instructions provided in the study Laboratory Manual, as soon as possible following collection. Samples will be shipped to Lumen Bioscience (Seattle, USA) for subsequent processing and analysis to determine the levels of drug product in the MLF. With the participant's approval, de-identified leftover samples may be stored at Lumen Bioscience indefinitely and used for future research studies related to the development of LMN-301. Detailed instructions for the collection, processing, storage and shipment of MLF samples for LMN-301 will be described in the study Laboratory Manual.

